2.0 Scientific Endpoints

2.1 *Describe the scientific endpoint(s), the main result or occurrence under study.*

*NOTE: Scientific endpoints are outcomes defined before the study begins to determine whether the objectives of the study have been met and to draw conclusions from the data. Include primary and secondary endpoints. Some example endpoints are: reduction of symptoms, improvement in quality of life, or survival. Your response should **not** be a date.*

Response:

The primary study outcomes are change in infants' FRR, zWFL, and home environments enrichment scores. The secondary outcome is infants' dietary intake.

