Participants' (both caregivers' and infant) weight will be assessed using a digital scale; participating parent's height will be assessed using a digital stadiometer and infant's length will be measured with an infantometer. We will request the participating parent to report the height and weight of the non-participating parent. Based on the height and weight data, BMI will be calculated according to the following formula: $BMI = \text{kg}/\text{m}^2$. For the infant, we will further calculate the BMI percentile and z-score, according to the World Health Organization Growth chart. For at-home height and weight measurement, participants will be provided a scale and a stadiometer, along with instructions on how to complete the procedure. Parents will be asked to take a photo of the child's weight on the scale and the stadiometer showing the child's height. The parent will take a photo of the parent's weight on the scale. Parents will then text the photos to the study's phone number or to the study's email account.

b) Demographic variables

Demographic and socioeconomic status will be assessed using the MacArthur Questionnaire developed by the MacArthur Foundation (San

Francisco, CA). This questionnaire assesses objective measures of socioeconomic status, including years of education, and subjective measures of the family's social standing in the community. Measurements also include both individual and household income levels, along with household size. Years of education will be coded separately for each parent, as well as developing a highest education score for each family.

c) Pregnancy History and Infant Feeding Practice Questionnaire

This questionnaire will be used to collect information about the pregnancy history of the mother, and the baby's current and future diet. The amount and type (i.e. breastfeeding, formula feeding, or mixed feeding) of feeding will be asked in this questionnaire too.

d) Baby Eating Behavior Questionnaire (BEBQ)

These 18 items questions are about baby's appetite over his/her first few months of life. This questionnaire specifically ask questions related to period during which baby was fed milk only, before the introduction of solid foods or prepared baby food.

e) Food Reinforcement Task

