. The questionnaire involves asking participants how much work they would do on 3 choice trials. The amount of work (i.e., button presses on a handheld counter) to earn snack foods increases with each choice, but the work required to obtain the alternative reinforcer, which is 10 min of watching a DVD, does not change. The same alternative, videos, is used for all choices so a common metric can be used to quantify all reinforcers. The snack food or alternative reinforcer choice begins at 20 button presses on the first trial, and responding increases by 20 presses on each successive trial for the snack food, with 640 presses required to obtain snack food on the last trial. The questionnaire will be used to assess reinforcing value of 1 out of 6 options of highly palatable, high energy-dense snack food that adult participants have chosen in previous studies and 2 non-food alternatives, which will include 1 physical activity and 1 sedentary leisure time activity, also chosen for a list of possibilities by the participant. Based on our experience using this questionnaire to test multiple reinforcing options in adults, we estimate 3 options would take

approximately 10 minutes. Since we will be including single parent families, we will only assess parental relative reinforcing value for one parent. The focus of data collection will likely be on the mother, as she is more likely to bring in the child than the father, and data suggest that maternal pre-pregnancy BMI is strongly associated with infant's weight. There is only one study on the relationship between parental and child food reinforcement, and this study focused primarily on maternal food reinforcement. There is no research on the relationship between parental and infant food reinforcement

i) Block Food Frequency Questionnaires (FFQ)

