18.0 Data Management and Analysis

18.1 *Describe the data analysis plan, including any statistical procedures. This section applies to both quantitative and qualitative analysis.*

Response:

Descriptive statistics will be determined, and the distribution of each variable will be examined to assess normality. Appropriate transformations based on the distribution will be considered prior to analysis. Mixed model analysis of covariance (ANCOVA) will be used to examine the changes in the motivation to eat versus motivation to engage in alternative behaviors (FRR), infant daily energy intake, zWFL and home environment between the music and control groups. All analyses will be intention to treat, and will include all families that are randomized. The primary outcomes will be analyzed using SAS PROC MIXED (mixed ANCOVA), which will include random intercepts and time effects clustered within participants, adjusting for any family, parental, and infant temperament confounders that are different between the groups. Mixed ANCOVA accounts for repeated observations over time of participants,

and allows analysis with missing data. The models examine group (music or control), time in months (0, 3, 6, etc.) and their interaction as class variables and planned comparisons will be done assessing group differences to specific measurement interval after randomization (3, 6, 12, and 24 months). FRR, daily energy intake, zWFL, and home environment enrichment score are expected to be different between groups from baseline through the 2-year study. We predict that the relative reinforcing value of music will increase as the program is extended from 6 weeks to one year, and the reinforcing value of food will decrease during the year of intervention. Since the intervention is designed to enrich the home environment to support greater involvement in music, we expect the increased reinforcing value of music and the decreased reinforcing value of food to be maintained during maintenance period. In addition, we predict infants in the music group will show less weight for length gain over time compared to the control group at 12 and 24-month assessments. All analysis will be computed using SYSTAT and SAS .

18.2 If applicable, provide a power analysis.

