NOTE: This may not apply to certain types of studies, including chart/records reviews, survey studies, or observational studies. This question is asked to elicit whether the investigator has an adequate sample size to achieve the study objectives and justify a conclusion.

Response:

The sample size for this proposal is based on the effect size of our pilot randomized controlled trial of an enriched music experience versus play dates on reducing relative food reinforcement and standardized weight for length in 9-15-month-old infants who were high in food reinforcement. Between groups differences in FRR showed an effect size (ESd) of 0.978. To detect differences for an ESd = 0.978 between the music and control groups with power at 0.80 and alpha at 0.05, 18 subjects per group are needed. The effects for standardized weight for length showed an ESd of 0.712 in zWFL differences between groups. Differences this large with power at 0.80 and alpha at 0.05 can be observed with 32 subjects per group. To be conservative, we will use a lower ESd = 0.667 for differences in infant weight (zWFL) change between groups. At power at 0.8 and alpha at 0.05, 37 subjects per group are needed. To control for attrition, we will recruit an additional 25% of parent-infant dyads at baseline, which will bring our total amount to be 46 subjects per group, or 92 subjects total. We feel as if this is a conservative estimate of treatment effects since this is a smaller effect size than we observed at six weeks in the pilot study, and we realistically think that the effects will be greater after a year of intervention.

18.3 Describe any procedures that will be used for quality control of collected data.

Response:

The primary investigator will be responsible for monitoring data safety at the weekly meetings. This includes ensuring confidentiality procedures are being followed in both recruitment and data collection. The types of data that will be monitored include demographic information and responses to questionnaires and assessments. The primary investigator will also be responsible for reporting serious events that occur during the laboratory sessions to the SBSIRB within 48 hours. The only anticipated serious event would be an allergic reaction to a food, previously unknown to the participant

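### Section 18.1 lets chance imbalance choose the covariates and leaves month-0 means free by arm; a short fixed list and a baseline-adjusted contrast would be a cheap improvement

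*Combined protocol and SAP*

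**What the plan says.** Section 18.1 specifies a mixed ANCOVA in SAS PROC MIXED with random intercepts and time effects, "adjusting for any family, parental, and infant temperament confounders that are different between the groups". It gives no list, no test or threshold, and no maximum number. Group is crossed with "time in months (0, 3, 6, etc.) and their interaction as class variables", so month 0 is one of the outcome times and each arm has its own month-0 mean. The baseline value of the outcome is not named as a covariate.

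The contrast is described in two ways. Section 2.1 says "The primary study outcomes are change in" FRR, zWFL and home enrichment scores. Section 18.1 says the model "will be used to examine the changes in the motivation to eat versus motivation to engage in alternative behaviors" (and the other outcomes). Section 18.2 sizes the trial "for differences in infant weight (zWFL) change between groups". Change from month 0 is therefore the main reading. The closing sentence on contrasts in section 18.1 nevertheless says "planned comparisons will be done assessing group differences to specific measurement interval after randomization (3, 6, 12, and 24 months", which could also mean the difference at each visit.

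**The concern.** In a randomised trial, an observed baseline difference carries no information about whether a variable is worth adjusting for; its relation to the outcome does. Under the stated rule the primary model cannot be written down until the arms have been compared, and two analysts could fit different models. A prognostic variable that happens to balance is left out. Section 10.2, in its account of the parental reinforcing-value questionnaire, notes that "data suggest that maternal pre-pregnancy BMI is strongly associated with" infant weight. Parental BMI is also derived at month 0 (section 10.2(a): "Based on the height and weight data, BMI will be calculated according to the following formula"), yet it would enter the zWFL model only if the arms happened to differ on it.

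Leaving month-0 means free has a separate cost. The change contrast then subtracts the whole baseline value, whatever its correlation with follow-up, where a baseline-adjusted contrast subtracts only the part that predicts follow-up. At stake are a primary model fixed in advance and some precision.

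**Working it through.** **1. The plan's own figure.** Inputs from section 18.2: ESd 0.667 on zWFL change, alpha 0.05, power 0.80. A two-sided noncentral t calculation gives power 0.808 at 37 per group and 0.797 at 36. The stated 37 is reproduced, as are 18 per group for ESd 0.978 and 32 for ESd 0.712.

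**2. How often chance selects something.** Assume 10 independent candidates and entry at p < 0.05 (neither is in the documents). The probability that at least one differs is 1 − 0.95^10 = 0.40. In simulations with 37 per arm, 10 to 15 candidates and that threshold, type I error under the rule stayed between 3.9% and 5.7%, so no inflation is shown.

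**3. Change versus baseline-adjusted contrast, complete data.** Let s0 and s1 be the SDs at month 0 and follow-up, and rho their correlation.

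- Var(change) ∝ s0² + s1² − 2·rho·s0·s1
- Var(adjusted) ∝ s1²(1 − rho²)
- Excess = (s0 − rho·s1)² / [s1²(1 − rho²)], which is never negative
- Effect size after adjustment = 0.667 × √(1 + excess)

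Example, s1/s0 = 1 and rho = 0.5: excess = 0.25/0.75 = 0.333; effect size = 0.667 × √1.333 = 0.770; power at 37 per group = 0.905.

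Both rho and the SD ratio are assumptions. Each cell shows excess variance, then power at 37 per group:

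| s1/s0 | rho 0.3 | rho 0.5 | rho 0.7 | rho 0.8 |
|---|---|---|---|---|
| 1 | 54%, 0.94 | 33%, 0.90 | 18%, 0.87 | 11%, 0.85 |
| 1.25 | 28%, 0.89 | 12%, 0.85 | 2%, 0.82 | 0%, 0.81 |

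At a ratio of 0.8 the excess is 56 to 99%, but nothing in the documents points to follow-up being less variable than baseline. Estimating the baseline slope costs about 1.4% of variance at N = 74, which the table ignores.

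**4. FRR.** Section 10.2(e) requires FRR > 0.5 at entry, which truncates the month-0 distribution. Assume that half of infants qualify and that scores are bivariate normal with equal SDs before truncation. The month-0 variance then falls to 1 − 2/π = 0.363 of its untruncated value, and the excess is 0.363 × (1 − rho)/(1 + rho). At untruncated rho of 0.3, 0.5, 0.7 and 0.8 this is 20%, 12%, 6% and 4%.

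**5. What a covariate main effect does to the change contrast.** With complete data and free month-0 means, a time-constant covariate shifts an infant's values equally at every visit and cancels from the change. In a numerical check with five visits, the month-24 change contrast was 0.4512 with and without two imbalanced covariates, while the difference at the visit moved from 0.245 to −0.294. Covariate choice therefore affects change only through covariate-by-time terms, a baseline constraint or missing data.

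**6. Cost of a useless covariate.** With p covariates unrelated to the outcome, variance is multiplied by 1 + p/(N − p − 3). At N = 74 the factor is 1.014, 1.044 and 1.076 for p = 1, 3 and 5. With the lost degrees of freedom, power falls from 0.808 to 0.802, 0.791 and 0.778.

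**7. Covariance structure under a common month-0 mean.** Assume a month-0/follow-up correlation of 0.1 and follow-up visits correlated 0.5. Month-24 variance relative to the plain visit difference is 0.99 with an unstructured covariance, 1.05 with random intercepts only, and 1.08 with intercepts plus a linear slope. With follow-up visits correlated 0.8, the last two become 1.17 and 1.33. The change contrast stands at 1.8 in both cases.

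**The case against.** The strongest reply is that nothing here is invalid. Free month-0 means are unbiased under randomisation, type I error holds and the sample size stands. Every gain depends on a correlation and an SD ratio that the documents do not give, and at a ratio of 1.25 with rho of 0.7 to 0.8 there is almost none. For FRR, power at ESd 0.978 with 37 per group is already 0.986. All of that stands, and it limits the point to prespecification and efficiency.

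Three further objections also stand. First, a reader might infer that fixing a prognostic covariate would by itself raise power noticeably. A main effect cancels from the planned change contrast with complete data, and the documents give no correlation between any covariate and change. Second, a reader might infer that the remedy can never lose precision. It can, if the list is long or uninformative, or if the month-0 constraint is combined with a random-intercept or linear-slope covariance and month 0 correlates weakly with follow-up. Weak correlation is plausible for FRR because of the entry rule. Third, the protocol's remark concerns maternal pre-pregnancy BMI and infant weight. Parental BMI at month 0 is a different measurement, in a parent who need not be the mother, and change in zWFL is a different outcome.

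The objection does not remove the rule itself: the primary model still depends on chance differences between the arms, and the contrast is still worded in two ways.

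**Conclusion.** The point holds as a cheap improvement. Section 18.1 should not let observed imbalance choose covariates, and it may leave precision unused by not adjusting for baseline. With complete data, the change contrast carries 0 to 54% more variance than a baseline-adjusted one over assumed rho of 0.3 to 0.8 and SD ratios of 1 to 1.25. For FRR the range is about 4 to 20% under the assumed truncation. Power at ESd 0.667 on change and 37 per group would go from 0.81 to between 0.81 and 0.94.

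A reader might go further and conclude that the rule biases the result, inflates type I error or undermines the 37 per group. The documents support none of these: the arms are randomised, simulated type I error stays near 5%, and the sample size reproduces.

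**What to change.** In section 18.1:

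- Delete the adjust-if-different rule.
- Fit PROC MIXED with a common month-0 mean and an unstructured covariance across visits, or adjust for the baseline outcome with a separate slope at each visit.
- State the contrast as the group difference at 3, 6, 12 and 24 months under that model. With a common month-0 mean this is also the difference in change, so the two wordings agree.
- Prespecify at most about three baseline covariates per outcome, chosen for expected relation to that outcome and used whatever the observed balance. For zWFL, parental BMI at month 0 is one candidate, with the caveat above about what the protocol supports. Enter them with covariate-by-time terms.
- State a rule for missing covariate values. PROC MIXED drops records without them, and section 18.1 promises to analyse every randomised family. This matters for temperament, since section 10.2 describes the IBQ-R for ages 3 to 12 months and infants enter at 9 to 15 months.
- Apply the month-0 constraint to IT-HOME only if its month-0 assessment precedes randomisation. Sections 10.1 and 11.2 leave that order unclear; settle it first.

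Cost: SAP wording and a small code change, using data already scheduled at month 0 (section 10.2 table), with no new families or visits. The statistical price is about 0.006 power for each covariate that proves unrelated to the outcome, hence the short list.

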1.0 Objectives

1.1 Describe the purpose, specific aims, or objectives of this research.

Response:

Specific Aim 1: To examine the effects of enhancing alternatives to eating on the motivation to eat or engage in alternative behaviors (the food reinforcement ratio or FRR) by using a music enhancement program.

Specific Aim 1a: To examine the effects of a music enhancement program on infant dietary intake.

Specific Aim 2: To examine the effects of a music enhancement program on infant weight status.

Specific Aim 3: To examine the effects of a music enhancement program on home environment enrichment score.

1.2 State the hypotheses to be tested, if applicable.

NOTE: A hypothesis is a specific, testable prediction about what you expect to happen in your study that corresponds with your above listed objectives.

Response:

We hypothesize that infants in the music enhancement program will have a lower FRR during the intervention and maintenance periods compared to control infants.

We hypothesize that infants in the music enhancement program will have a lower daily energy intake during the intervention and maintenance periods compared to infants in the control arm.

We hypothesize that infants in the music enhancement program will have a lower weight for length z-score (zWFL) during the intervention and maintenance periods compared to infants in the control arm.

We hypothesize that infants in the music enhancement program will have a more enriched home environment during the intervention and maintenance periods compared to infants in the control arm.

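### The mixed model leaves the month-0 group means free and names no adjustment for the baseline outcome; a common month-0 mean would use data already collected and could sharpen the estimates at almost no cost

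*Combined protocol and SAP*

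**What the plan says.** Section 18.1 specifies a mixed ANCOVA in SAS PROC MIXED. Its fixed effects are described as follows: "The models examine group (music or control), time in months (0, 3, 6, etc.) and their interaction as class variables". The covariance part is one "which will include random intercepts and time effects clustered within participants". The only adjustment named is "adjusting for any family, parental, and infant temperament confounders that are different between the groups". Neither a baseline-outcome covariate nor an equality of month-0 means appears anywhere in the document.

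The target of the planned comparisons has to be inferred:

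- Section 2.1 points to change: "The primary study outcomes are change in infants' FRR, zWFL, and home environments enrichment scores".
- Section 18.1 also points to change, saying the model "will be used to examine the changes in the motivation to eat versus motivation to engage in alternative behaviors (FRR") and the other outcomes. Section 18.2 bases the sample size on zWFL change.
- Section 1.2 words the hypotheses as levels. For example, infants in the music arm "will have a lower weight for length z-score (zWFL) during the intervention and maintenance periods compared to infants in the control arm".
- The sentence that should settle it says only that "planned comparisons will be done assessing group differences to specific measurement interval after randomization (3, 6, 12, and 24 months"), without saying how month 0 enters.

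Section 18.1 also commits that "All analyses will be intention to treat, and will include all families that are randomized".

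**The concern.** Section 10.1 places random assignment after baseline data collection. For outcomes measured by then, the two arms have the same expected month-0 mean by design. A model that estimates the two means separately ignores this. Subtracting baseline from follow-up amounts to fixing the regression slope of follow-up on baseline at 1, whereas a baseline-adjusted comparison estimates that slope. When the true slope is not 1, the change comparison carries avoidable noise.

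What is at stake is precision only. It matters most for zWFL, which sets the sample size and whose planned power is barely above 0.80. FRR has ample power at its own planned effect.

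**Working it through.** **Inputs from the documents (Section 18.2).** Effect size 0.667 for zWFL change, alpha 0.05, power 0.80, 37 per arm evaluable, 46 per arm recruited; effect size 0.978 for FRR.

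**Inputs assumed.** r is the correlation between baseline and follow-up. k is the baseline SD divided by the follow-up SD. The effect size 0.667 is taken in units of the SD of change.

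**Step 1: reproduce the plan's figure.** A two-sample, two-sided noncentral-t calculation with d = 0.667 gives power 0.797 at 36 per arm and 0.808 at 37, so the stated 37 is reproduced. FRR (d = 0.978) at 37 per arm has power 0.986.

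**Step 2: compare the two contrasts.** Set the follow-up variance to 1 and the baseline variance to k². Per infant:

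- change: variance = 1 + k² − 2rk
- baseline-adjusted: variance = 1 − r²
- ratio (change / adjusted) = (1 + k² − 2rk) / (1 − r²) = 1 + (k − r)² / (1 − r²)

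The ratio is never below 1 and equals 1 only when k = r. For example, k = 1 and r = 0.6 give (2 − 1.2)/(1 − 0.36) = 0.80/0.64 = 1.25.

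**Step 3: zWFL power at 37 per arm.** The adjusted contrast has effective d = 0.667 × √ratio on 71 df. Power for the change contrast is 0.81 throughout.

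| k | Ratio at r = 0.4 / 0.5 / 0.6 / 0.7 / 0.8 | Adjusted power, lowest to highest |
|---|---|---|
| 0.6 | 1.05 / 1.01 / 1.00 / 1.02 / 1.11 | 0.81 to 0.85 |
| 0.8 | 1.19 / 1.12 / 1.06 / 1.02 / 1.00 | 0.81 to 0.87 |
| 1.0 | 1.43 / 1.33 / 1.25 / 1.18 / 1.11 | 0.85 to 0.92 |
| 1.2 | 1.76 / 1.65 / 1.56 / 1.49 / 1.44 | 0.93 to 0.96 |

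**Step 4: check against the repeated-measures model.** Take visits at 0, 3, 6, 12 and 24 months with a random intercept and a linear random slope, which is one reading of Section 18.1. Assume intercept variance 0.7, residual variance 0.3 and a slope contribution of 0.5 at month 24. Generalised least squares with a common month-0 mean has the same variance as the baseline-adjusted contrast. The ratios at months 3 / 6 / 12 / 24 are 1.17 / 1.17 / 1.14 / 1.09. At month 24 (r = 0.57, k = 0.82) the ratio becomes 1.29 with an intercept–slope covariance of −0.2 and 1.01 with +0.2, on the 24-month scale.

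**Step 5: families with baseline only.** Suppose 46 − 37 = 9 families per arm give no follow-up. The free-mean change contrast then has variance (1 − r²)·2/37 + (k − r)²·2/46, against (1 − r²)·2/37 for the adjusted one. At k = 1 the ratio is 1.34 at r = 0.4 and 1.09 at r = 0.8.

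**Step 6: FRR.** Section 10.2 e) defines high food reinforcement as FRR above 0.5, so baseline FRR is truncated. Assume bivariate normality with equal variances before selection, correlation 0.4 to 0.8, and 30% to 70% of infants above the cut. Then k falls to 0.55–0.85 and the ratio is only 1.03 to 1.21.

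**Step 7: the cost when there is nothing to gain.** At k = r = 0.8, simulation of 20,000 trials with the slope estimated gives power 0.806 for change and 0.800 for adjusted, a loss of under one point. At r = 0.6 the simulated powers (change / adjusted) are about 0.81 / 0.83, 0.81 / 0.88 and 0.80 / 0.94 for k = 0.8, 1.0 and 1.2, in line with Step 3.

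**The case against.** The strongest reply is that this is a preference about efficiency. Group, time and group-by-time with month 0 as a response is a standard and valid way to estimate change, and change is what Section 2.1 names. That is correct, and the point is not put as an error.

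The size of the gain is also uncertain. The documents give neither r nor k, nor the SD by which 0.667 was standardised. If it is in follow-up SD units with k = 1, power (change / adjusted) is 0.73 / 0.87 at r = 0.4 and 0.99 / 1.00 at r = 0.8. If all 46 per arm contribute, change power is 0.89 rather than 0.81. Section 10.1 allows parent-taken and pediatrician-supplied measurements. If these add error variance of 0.25 at follow-up, the k = 1 ratios shrink from 1.43–1.11 to 1.33–1.07. All of this stands, and it affects the size of the gain only.

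Two further replies concern the reading. The label "mixed ANCOVA" might imply baseline adjustment, but the written model has no baseline-outcome term. Alternatively, the comparison may be of unadjusted levels at each visit. In that case power at 37 per arm (k = 1, 0.667 in change-SD units) would be 0.87 at r = 0.4 but 0.43 at r = 0.8. The same remedy would then help through a variance ratio of 1/(1 − r²), which is 1.19 to 2.78 over that range. The ambiguity is a reason to define the contrast; it does not remove the point.

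**Conclusion.** The concern holds as an improvement the plan should adopt, with medium confidence. As written, the month-0 means are free and no adjustment for the baseline outcome is specified. Read as a change analysis, the plan is valid and the sample size of 37 per arm is not wrong on this account.

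For zWFL, baseline adjustment could raise power from 0.81 to between 0.85 and 0.92 if the SDs are equal and r lies between 0.4 and 0.8. The gain is nil when k = r and larger when baseline is more variable than follow-up. These are illustrative ranges resting on assumed r, k and standardiser, not an expected loss. For FRR the benefit is modest.

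**What to change.** Add one sentence to Section 18.1 defining the planned comparison as the baseline-adjusted group difference at months 3, 6, 12 and 24. In the existing PROC MIXED model, give both arms a common month-0 mean. This form keeps every randomised family, including those with baseline data only.

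Apply the constraint only where the month-0 measure precedes randomisation. FRR determines eligibility, and anthropometrics and dietary recalls are collected during screening, so these qualify. IT-HOME is unclear: Section 10.1 puts randomisation after baseline data collection but then names the month-0 IT-HOME visit and randomisation together, and Section 11.2 places that visit after eligibility without saying whether allocation has occurred. Confirm the order, and leave IT-HOME unconstrained if the visit can follow allocation.

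For FRR, because its baseline is truncated, an acceptable alternative is to model months 3 to 24 with baseline FRR and its interaction with time as covariates. That form omits families with no follow-up and would have to be reconciled with the commitment to include all randomised families.

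The cost is one sentence and a small change to the model statement, with no new data; if the true gain is zero, under one point of power is lost.
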